#### 5.2.2 Retention

The study retention plan will incorporate multiple interventions to achieve a retention rate greater than 70%. Contact information will be collected from each participant, including email and mobile phone number verification. The study will allow participants to schedule their preference for when (e.g., afternoon, evening) they would like to receive prompts to complete electronic follow-up surveys. Participants are more likely to complete surveys if they are alerted about them at a time they can complete the survey. At enrollment, study staff will ask permission for several means of contacting participants and ask for updated information on each follow-up survey. Retention contacts will be customized based on participants' contact preferences (email, text, call, US mail) and organized on a database platform called Study Management and Retention Tool (SMART), a secure system accessible only to designated study staff. Participants will be asked about any changes in their contact information or plans to move during each follow-up survey, conducted at 3-month intervals.

Follow-up methods include sending electronic notification reminders to the participant up to 3 times if a survey remains uncompleted. If after the 3rd notification, the assessment has

still not been completed, then the retention activities will escalate to a staff member. Depending on the participant's preferences provided upon registration, contacts will be made initially with the preferred mode of re-contact (for example, SMS); if still unresponsive, other available modes (e.g., phone call, private social media messages) will be used. Each contact is logged in an electronic retention system developed by Emory. The system maintains electronic lists of each participant's retention status and automatically creates notification lists for retention staff to ensure that a systematic process is followed and documented for retention.

If contact with participants is lost (missed surveys or appointments and non-responsive to contact requests), we will have obtained consent to use public-use databases (e.g., Lexis-Nexis) to locate participants. Study staff will check for entry into a jail or prison in the jurisdiction from which the participant was recruited (i.e., Atlanta, GA, Jackson, MS, or Washington, D. C.). For participants who cannot be contacted, after IRB approval staff will attempt to link the identities of participants to registries of known decedents using a statewide dataset (vital records) and a nationwide dataset (National Death Index).

# 5.2.3 Participant Compensation

Compensation for survey completion will be graduated (\$50 baseline, \$40 months 3 and 6, \$50 month 9, \$60 month 12). Study incentives for the baseline will be sent 48-72 hours after completion of the baseline survey to allow for review of data and identification of possible fraudulent or duplicate enrollments. Incentives for IDIs and quarterly follow-up surveys will be processed electronically at the time of interview or survey completion (see Fraud Deterrence). Men in both arms will be asked monthly if they have initiated PrEP; men who report initiating PrEP in either arm will be mailed a dried blood spot collection kit with instructions and a prepaid return mailing envelope, and will be directed to collect and mail a dried blood spot specimen for tenofovir diphosphate detection. Those who return a DBS specimen will be provided with an additional compensation of \$40. Participants will also be asked to take a picture of their prescription or PrEP label; those who provide a photograph will be provided with an additional compensation of \$15. A maximum compensation of \$295 could be provided for completing all of the study visits (\$240), DBS specimen (\$40), and PrEP prescription photo verification (\$15).

#### 5.3.4 Fraud deterrence and detection

Fraudulent responses in research are of concern in all settings, and there are particular vulnerabilities in online research. In order to avert fraudulent registrations details of eligibility criteria will not be reported before screening, IP addresses will be tracked to block duplicate screening attempts, and Captcha will be used to avoid bots. Payment of initial baseline incentives will be delayed for 48-72 hours to allow us to perform automated scans for duplicate IP addresses, names, duplicate email addresses, or phone numbers. In these cases, study staff will attempt to resolve concerns by contacting participants and clarifying how the situation arose. If duplicate registrations are detected, records will be inactivated and deemed to be invalid.

# 5.3 Treatment Assignment Procedures

#### 5.3.1 Randomization Procedures

After providing informed consent, downloading the study application, and passing the fraud check, participants will be randomized to study arms in a 2:1 ratio of intervention to control arms (rationale: to allow sufficient data on app users to allow for analysis of efficacy by level of app usage), stratified by MSA to ensure balance of the study arms across the three study sites. Within each city stratum, a computer program will randomly assign each participant to the next treatment allocation from a random-permuted block randomized sequence. Once participants are randomized, they will be kept in and analyzed according to their original assignment (i.e., intent-to-treat). Participants who are not verified as legitimate or are unable to download the app will not be randomized into the study.

# 5.4 Subject Withdrawal

Participants may voluntarily withdraw from the study for any reason at any time. The study investigators also may withdraw participants from the study in order to protect participant or staff safety. Study staff will record the reasons for all withdrawals or holds from the study on a Study Stop Form in the participants' study records.

Participants who seroconvert will be asked to participate in in-depth interviews (IDI). All of the participants will be followed per standard protocol for linkage to care. Participant will then be withdrawn from study activities.

#### **6 STUDY INTERVENTION**

#### 6.1 Study Product Description

HealthMindr is a mobile app with HIV prevention information and links to services developed specifically for MSM. A summary of the key features of the app is provided below.

Functions included in the HealthMindr app:

- HIV testing: learn more about testing options; make a plan to test 2-4 times in the coming year; locate possible places for those tests; and schedule reminders (goal setting).
- Behavioral risk assessment: short behavioral risk assessment (e.g., HIV risk behaviors: sex while drunk or high, condomless anal intercourse with a positive or unknown HIV status partner, total number of sex partners, recent STI diagnosis, use of methamphetamine or poppers) and protective behaviors (HIV testing, STI testing, consistent condom use; feedback/self-regulation).
- Non-occupational post-exposure prophylaxis (nPEP): information about nPEP; nPEP self-assessment; nPEP locator; referral to PrEP for men who evaluate multiple exposures for nPEP indication (goal setting and outcome expectation). 
- Product ordering: Via the app, users can order condoms, condom-compatible lubricant, and at-home STI specimen collection kits (urethral and rectal gonorrhea and chlamydia, syphilis) and at-home HIV test kits (OraQuick; goal setting). Orders are filled automatically through Amazon fulfillment services.
- Pre-exposure prophylaxis: PrEP self-assessment at first app use; monthly rescreening for PrEP eligibility; recommendation for PrEP based on CDC criteria; PrEP provider

locator; transport or driving directions to providers, and PrEP FAQ. The PrEP self-screener assesses certain key elements of behavioral eligibility (potential indicators of "ongoing, high risk for HIV acquisition"), and recommends potentially eligible MSM visit a PrEP provider for further clinical assessment, with help locating nearby providers and transport directions (self-efficacy, goal setting and outcome expectations).

• Substance Use Directory: a list of local resources available for treatment, rehab, and counselling options will be accessible through the app.

#### 6.1.1 Acquisition

After completing the eligibility screener and informed consent (Appendix B), participants will be directed to a link to authenticate their smartphone and download the HealthMindr App from either Google Play or Apple App Store. All participants will view the same app shell and complete the baseline survey in the app. However, once randomized, the app for those marked as intervention will open up to show all HealthMindr app capabilities. The app information will cover the importance of testing, links to HIV prevention resources, resources to locate HIV testing and PrEP services, the SAMHSA substance abuse treatment resource locator, and other prevention information specific to their area. The app for the control arm will allow study staff to interact with them via the SMART system. The control-arm app will display a study event timeline but none of the HIV prevention information contained in HealthMindr app.

The HealthMindr application will prompt the intervention participants to complete a brief PrEP assessment (monthly). Any notifications directed to a phone's lock screen or to a participant's SMS/text message account can be partially viewed by unauthorized users of the phone and will be generic text (e.g., "You have a message waiting for you."). To ensure that app notifications protect the privacy and discretion of participants, all app and text notifications will be stated generally, with no reference to the content of the message, the nature of the message, the content of the app in general, the name of the study, or any reference to HIV, STI or MSM. The lock screen banner notification will indicate only that the notification is for the HealthMindr app. SMS/text message notifications will similarly alert participants that a new message is available in HealthMindr. Absolutely no content referring to sensitive topics will be exposed without directly entering the app. The same notification format will be used for both intervention and control groups.

Every three months, participants will be asked to complete a follow-up survey similar to the initial baseline survey. The follow-up survey will include questions on demographic characteristics, HIV and STI testing history and status, and condom use, PrEP use and adherence, knowledge, perceptions, beliefs, intents, communication with sex partners, substance use, mobile phone and data usage, access to internet and information, as well as psychosocial cofactors. If the participant has any questions regarding study activities, they will be connected with study staff. Study staff will handle any research related questions or issues with the participant.

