# **PROTOCOL SUMMARY**

Title:	HealthMindr: Theoretically based mobile app to increase PrEP uptake among MSM
Précis:	The study is based on the premise that providing, through a mobile phone app, self-directed PrEP information; periodic PrEP eligibility screenings to identify risk and eligibility objectively; referral to PrEP providers with directions; and related prevention services will increase the uptake of PrEP among at risk, HIV-negative MSM to a greater extent than standard of care referrals to existing resources.
Objectives:	Aim 1: Test an HIV prevention mobile app versus a standard of care condition with outcome of rate of PrEP uptake among MSM.
	Aim 2: Quantify the behavioral, social, and clinical factors that mediate and moderate the efficacy of the HealthMindr app on the rate of PrEP uptake.
	Aim 3: Conduct individual in-depth interviews (IDIs) to assess how the app promoted PrEP uptake, unmet needs of men who did not start PrEP, and how repeated app interactions might further PrEP uptake.
Population:	680 MSM, aged 18-34
Sites:	Atlanta, GA; Jackson, MS; and Washington, DC
Intervention:	HIV prevention mobile app with basic prevention services including HIV test planning and test locators; risk assessment; HIV treatment locators; and condom, HIV test kit, and at-home STI specimen collection kit distribution plus monthly PrEP eligibility assessments, PrEP provider locator, enhanced information about PREP, and referrals to local PrEP navigators.
Study Duration:	60 months
Subject Participation Duration:	12 months
Estimated Time to Complete Enrollment:	18 months

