#### 9.1.1 Adverse Events

- 1. Participant report of loss of confidentiality through the app or its functions
- 2. Participant report of loss of confidentiality through delivery of prevention supplies or commodities
- 3. Participant report of access by others to protected health information through the app or study procedures.
- 4. Participant report of disclosure of status as a research participant due to study-related reminders (from app, phone calls, emails, or text messages).
- 5. Participant report of discomfort or injury due to use of provided specimen collection materials (e.g., finger stick for syphilis testing, self-administered rectal swab or pharyngeal swab).
- 6. Disclosure of personal information about health, sexuality or sexual practices that results in physical violence or threat of violence.
- 7. Disclosure of personal information about health, sexuality or sexual practices that results in adverse effects on employment

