# 14.1 Recontacting Past Participants

Participants who reported PrEP initiation on a monthly check-in survey but not a quarterly survey (primary study outcome) will be contacted for clarification. Only the participants who previously provided consent to be recontacted will receive a message. A \$20 compensation in the form of electronic gift code will be given to those participants who respond.

Voicemail: Hi, this is [insert your name] calling from Emory with the HealthMindr study. You have reported starting PrEP during our research study, but you also reported that you have not started PrEP in surveys afterwards. I was hoping to verify some information from your time in the study. You are eligible to receive additional compensation for your response. You can call us back at [phone number]. Or feel free to text me and let me know what the best time is for a call. Thank you!

Phone Script: Hello, may I speak with [PARTICIPANT'S NAME]? My name is [insert your name]. I am with Emory working on the HealthMindr study. You have reported starting PrEP during our research study, but you also reported that you have not started PrEP in surveys afterwards. According to your survey, you reported PrEP usage in [MONTH/YEAR]. Is this correct? Did you stop taking PrEP any time after?Thank you for your clarification. Also for the compensation, we will send you a \$20 gift code. Do you have a preferred store? We have gift codes from Amazon, Target and Walmart.That is all the questions I have and thank you for participating in our research study!

Text Message: Hello! This is [NAME] from the Emory HealthMindr study. We were hoping to get you on a call for a few minutes to to verify some information from your time in the study and you will be compensated for your time. What time works best for you for a short phone call?

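### Section 6.1.1 bars the study's name from all app and text notifications, then has the lock-screen banner and text messages name HealthMindr, which is also the study's name.

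*Combined protocol and SAP*

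**What the plan says.** Section 6.1.1 (Acquisition) starts from the risk that someone else may see part of a lock-screen or text notification. It calls for generic text and gives an example that says only that a message is waiting. It then sets the rule: "all app and text notifications will be stated generally, with no reference to the content of the message". The list of barred content goes on to include "the content of the app in general, the name of the study, or any reference to HIV, STI or MSM".

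Two sentences on delivery follow directly:

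- Banner: "The lock screen banner notification will indicate only that the notification is for the HealthMindr app".
- Text message: "SMS/text message notifications will similarly alert participants that a new message is available in HealthMindr".

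The section ends by giving both arms the same notification format.

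Elsewhere the same word names the study. The title in the Protocol Summary is "HealthMindr: Theoretically based mobile app to increase PrEP uptake among MSM", and the text-message script in section 14.1 introduces the caller as "from the Emory HealthMindr study". Section 6.1 describes the product: "HealthMindr is a mobile app with HIV prevention information and links to services developed specifically for MSM". Item 4 of the adverse event list in section 9.1.1 is "Participant report of disclosure of status as a research participant due to study-related reminders".

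**The concern.** The ban is absolute and covers the study's name. The delivery sentences then require a word that serves as both the app's name and the study's name. Whoever writes the message templates has to break one instruction to follow the other.

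What is at stake is confidentiality. The protocol treats visible notifications as a route by which others may learn of participation, and it counts the resulting disclosure as an adverse event. Section 16.2 also commits staff to limiting indirect disclosure that a man is in an HIV-related study or in one that enrols MSM. A name that a bystander recognises or looks up is a form of indirect disclosure. Control participants receive the same notifications without the app's prevention content. Eligibility, randomisation, outcome definition, power and analysis are unaffected.

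**Working it through.** The plan states no figure to reproduce. The check is a comparison of text, followed by a count of exposures.

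**1. The texts side by side**

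| Place | What it requires or shows |
|---|---|
| 6.1.1, rule | No study name in any app or text notification |
| 6.1.1, example | Generic text with no app or study name |
| 6.1.1, banner sentence | Names HealthMindr |
| 6.1.1, text-message sentence | Names HealthMindr |
| Protocol Summary, title | HealthMindr is the lead name |
| 14.1, participant scripts | HealthMindr is used as the name of the study |
| 16.2, sample push notifications | Generic, HealthMindr not named |

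If HealthMindr is the study's name, the third and fourth rows break the first. The title and the section 14.1 scripts show that it is. No other section resolves the conflict. The second and last rows show that the protocol already contains wording that complies.

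**2. The route to disclosure**

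The word itself mentions neither HIV, MSM nor research. A bystander has to know it or look it up. The documents give no probability for that step, so no number of disclosures can be calculated.

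**3. Exposure count**

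Inputs: 12 months of participation and 680 men (Protocol Summary); monthly surveys in both arms (sections 4 and 7.3); quarterly surveys at months 3, 6, 9 and 12 (section 7.3).

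- Monthly and quarterly prompts sent separately: 12 + 4 = 16 first prompts per man.
- Merged in the four months where they coincide: 12 per man.
- Over 680 men: 680 × 12 = 8,160 to 680 × 16 = 10,880 first prompts.

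Section 5.2.2 adds up to three electronic reminders when a survey is not completed. It does not say whether the monthly surveys are covered. With separate prompts, and three reminders on top of each first prompt that qualifies:

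- Reminders on quarterly surveys only: 12 + 4 × (1 + 3) = 28 per man; 680 × 28 = 19,040.
- Reminders on all prompts: 16 × (1 + 3) = 64 per man; 680 × 64 = 43,520.

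Both figures with reminders are ceilings. They assume that every reminder is used for every survey concerned and that nobody leaves, whereas section 12.2 assumes 20% annual attrition. Section 5.2.2 also allows contact by email, call or post, so not every contact need be a banner or a text.

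**The case against.** The best defence is that the two delivery sentences put the rule into practice. On this view the app's name is the permitted minimum, distinct from the study's name. The banner sentence says that only the app will be indicated, and the title can be read as naming the app. The section 14.1 scripts are for recontacting past participants, not for routine prompts. This does not remove the conflict. The rule is worded without exception, the example beside it carries no name, and the trial's own scripts use the app's name for the study. If an exception was meant, it is not written.

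The second objection is that the risk is already managed, and this stands in part. Under section 16.2, staff ask for each contact mode whether others have access and whether a non-specific message is acceptable. Scripts go to the IRB, push notifications are generic, sensitive inbox messages need a PIN, and the app requires re-authentication. Section 15.1.1 has men encouraged to delete study emails and texts, and section 5.2.2 lets them choose the time and mode of contact. These measures lower the risk, but they do not reconcile the two rules.

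Three stronger readings are tempting, and the documents do not support them:

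- A reader might infer that the prompts reveal MSM status and that the adverse event list names this harm. Item 4 of section 9.1.1 concerns status as a research participant. What a bystander would learn by looking up the name is not in the documents; section 6.1 is the protocol's own internal description.
- A reader might take 64 messages per man, or 43,520 overall, as the size of the problem. That extends the section 5.2.2 reminders to monthly prompts without support in the text, and a count of messages does not measure harm.
- A reader might conclude that the app must be renamed. That means changing a product distributed through two app stores, and a replacement name could be looked up too.

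**Conclusion.** The contradiction within section 6.1.1 is real, and nothing elsewhere in the protocol settles it. It rests on one reading, that HealthMindr counts as the study's name, which the title and the section 14.1 scripts support.

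The consequence is a possible, indirect disclosure of research participation, with no known rate and with partial safeguards in place. The exposure is about 12 to 16 first prompts per man, assuming full follow-up. The totals of 28 or 64 with reminders depend on an assumption about which surveys are chased. The correction is worth making because it costs little and the protocol itself promises the safeguard without exception. The trial's statistical conclusions do not depend on it.

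**What to change.** In section 6.1.1:

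- Replace the text-message sentence with one requiring the section's own generic example, with no app or study name.
- Require the same text in the body of the lock-screen banner.
- Where the phone system puts the app's label on the banner, state this as an explicit exception to the study-name rule, and tell participants about it at enrolment.

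A neutral display name for the app is optional and is not needed to resolve the conflict.

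The cost is an edit to the message templates, a short protocol amendment with the IRB review that section 15.3 requires, and a line in the enrolment material. The downside is that some men may not recognise the sender at first; a line at enrolment explaining what the messages look like can cover this.

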#### 7 STUDY SCHEDULE

#### 7.1 Screening

After a potential participant is determined to be eligible and agrees to participate, they will be asked to provide their contact information including name, primary phone number and primary email address. The phone number and email address will be used as a measure against

participant fraud. If a participant does not provide valid and unique contact information, they will not be able to sign in to the app until they have provided it. If a participant provides contact information that matches that of another registrant, they will be rejected administratively.

